11.3.2.3 Control of Bleeding

For each subject, achieving control of bleeding is defined as having 0 days of bleeding and up to 1 day of spotting during the last 28 days prior to and including the Reference Day with the interval starting from Study Day 11. The control of bleeding analysis will include subjects with at least 38 days prior to and including the Reference Day. If a subject did not have evaluable AH data during the last 28 days and no bleeding or spotting

or "There was no visible blood on the sanitary products" was indicated on UBQ, then the subject is considered having achieved control of bleeding. If the subject indicates bleeding or spotting on the UBQ, the subject does not meet the criteria for control of bleeding.

The number and percentage of subjects achieving control of bleeding will be summarized by treatment group and will be compared between each of the elagolix dose groups and placebo using a Pearson's chi-square test or Fisher's exact test (if $\geq 20\%$ of the cells have expected counts less than 5).

11.3.3 Bleeding Days

The numbers of bleeding days by intensity categories (Section 7.6.2) will be calculated for each 28-day interval starting at Study Day 2 up to Study Day 168 in the Treatment Period (i.e., Study Days 2 – 28, Study Days 29 – 56, Study Days 57 – 84, Study Days 85 – 112, Study Days 113 – 140, and Study Days 141 – 168) and the first 28-day interval in the Post-Treatment Follow-up Period (i.e., Study End Days 1 – 28) for each treatment group. For each 28-day interval, each analysis includes subjects who did not prematurely discontinue in or before this 28-day interval. For example, for Study Days 29 – 56, it includes subjects who were on treatment for at least 56 days. For Final Month analysis, it includes subjects who were on treatment for at least 38 days prior to and including the Reference Day. The summary of average number of bleeding days in a 28 day window during the Treatment Period will be provided for each treatment group by intensity categories. No statistical tests will be performed.

A summary of average number of days by bleeding intensity categories in each 28-day interval during the treatment period will be provided for the following four populations, respectively: 1) the subjects with > 0 bleeding days in Month 1 (Study Days 2 – 28); 2) the subjects who did not bleed (0 bleeding days) in Month 1 (Study Days 2 – 28); 3) the subjects with > 0 bleeding/spotting days in Month 1 (Study Days 2 – 28); 4) the subjects with 0 bleeding/spotting days in Month 1 (Study Days 2 – 28).

If a subject did not have evaluable AH data during an interval and no bleeding was indicated on UBQ ("Subject only has spotting that did not require the use of sanitary products" or "There was no visible blood on the sanitary products" was allowed), then the number of bleeding days over the interval is 0. The number and percentage for each treatment group and overall will be provided for subjects who did not have evaluable AH data during an interval and bleeding was indicated on UBQ.

The change and percent change from Baseline in the numbers of bleeding/spotting days to each 28-day interval and Final Month in the Treatment Period and the first 28-day interval in the Post-Treatment Follow-up Period will be summarized for each treatment group, respectively. The comparison between each elagolix dose group and placebo will be performed using a one-way ANCOVA method with treatment as the main effect and Baseline as a covariate for the Treatment Period only. The same analysis will be performed for bleeding days as well.

11.3.4 Hemoglobin Concentration

Hemoglobin (Hgb) concentration data will be summarized as observed; missing data will not be imputed.

Baseline Hgb concentration is defined as the last measurement prior to or on the first dose date of study drug. The change and percent change from Baseline in Hgb concentration to Months 1 – 6 during the Treatment Period will be analyzed with one-way ANCOVA with treatment group as the main effect and Baseline as a covariate.

The number and percentage of subjects with changes in Hgb concentration from Baseline to Months 1 – 6 during the Treatment Period in each of the following categories will be summarized by treatment group and compared between each elagolix dose group and placebo, using a Pearson's chi-square test or Fisher's exact test (if $\geq 20\%$ of the cells have expected counts less than 5).

- Change from Baseline in Hgb ≤ -1.0 g/dL
- -1.0 g/dL < Change from Baseline in Hgb ≤ -0.5 g/dL

- $-0.5 \text{ g/dL} < \text{Change from Baseline in Hgb} < 0.5 \text{ g/dL}$
- $0.5 \text{ g/dL} \leq \text{Change from Baseline in Hgb} < 1.0 \text{ g/dL}$
- $1.0 \text{ g/dL} \leq \text{Change from Baseline in Hgb} < 1.5 \text{ g/dL}$
- $1.5 \text{ g/dL} \leq \text{Change from Baseline in Hgb} < 2.0 \text{ g/dL}$
- $\text{Change from Baseline in Hgb} \geq 2.0 \text{ g/dL}$

Also, shift tables from Baseline to Month 3 and Month 6 will be summarized by the following categories.

- $\text{Hgb} \leq 10.5 \text{ g/dL}$
- $10.5 \text{ g/dL} < \text{Hgb} \leq 12 \text{ g/dL}$
- $\text{Hgb} > 12 \text{ g/dL}$

The number and percentage of subjects who had Hgb Baseline $\leq 10.5 \text{ g/dL}$ and have an increase in Hgb concentration $> 2 \text{ g/dL}$ from Baseline will be summarized for each month by treatment group and compared between each elagolix dose group and placebo, using a Pearson's chi-square test or Fisher's exact test (if $\geq 20\%$ of the cells have expected counts less than 5). The number and percentage of subjects who had Hgb Baseline $\leq 10.5 \text{ g/dL}$ and have an increase in Hgb concentration $> 1 \text{ g/dL}$ from Baseline will be summarized for each month by treatment group and compared between each elagolix dose group and placebo, using a Pearson's chi-square test or Fisher's exact test (if $\geq 20\%$ of the cells have expected counts less than 5).

In addition, the number and percentage of subjects who have an increase in Hgb concentration $> 1 \text{ g/dL}$ from Baseline will be summarized for each month by treatment group and Baseline Hgb concentration categories as follows. Same summary will be provided for increase in Hgb concentration $> 2 \text{ g/dL}$ from Baseline to each month.

- $\text{Hgb} \leq 10.5 \text{ g/dL}$
- $10.5 \text{ g/dL} < \text{Hgb} \leq 12 \text{ g/dL}$
- $\text{Hgb} > 12 \text{ g/dL}$

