4.3 Sample Size

Approximately 400 subjects will be randomized in a 1:1:2 ratio to placebo (N = 100), elagolix 300 mg BID (N = 100), or elagolix 300 mg BID plus E2/NETA (N = 200). The sample size will provide at least 90% power to detect a difference between the elagolix 300 mg BID plus E2/NETA group and the placebo group in the percentage of subjects with menstrual blood loss (MBL) volume < 80 mL during the Final Month (as defined in Section 7.2) and 50% or greater reduction in MBL volume from Baseline to the Final Month under the assumption of responder rates being 60% and 30% for elagolix 300 mg BID plus E2/NETA and placebo, respectively. The sample size determination is primarily driven by the need for a sufficient number of patients for the safety database. The above sample size was calculated using nQuery advisor 7.0.

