11.0 Efficacy Analysis

11.1 General Considerations

Unless otherwise stated, all statistical tests will be conducted at an alpha level of 0.05 (two-sided). A test will be deemed significant if the *P* value rounded to three decimal places is less than or equal to 0.05, unless otherwise specified. For analyzing efficacy variables, each elagolix dose group will be compared with placebo. The elagolix dose groups will not be compared against each other unless otherwise specified. The primary efficacy comparison will be between the elagolix 300 mg BID plus E2/NETA group and the placebo group. The comparison between the elagolix 300 mg BID alone group and the placebo group will be used as a reference and to examine the validity of the study design.

Unless otherwise specified, categorical data will be summarized by frequency and percentage; descriptive summaries of continuous data will display the mean, SD, median, minimum, and maximum.

For continuous variables, when the analyses of change and/or percent change from Baseline to post-baseline visit(s) are performed, the within-group change from Baseline to each relevant visit will be summarized by treatment group with the mean, SD, and 95% Confidence Intervals (CIs). The between-group differences will be summarized with the

mean, SE, 95% CIs, and *P* value when applicable. At each post-baseline visit, the Baseline mean and post-baseline visit mean will be calculated for all subjects with baseline and post-baseline value at that visit by treatment group.

Information regarding corresponding statistical methods for analyses and any additional statistical measures required for a specific variable/endpoint are provided in the relevant sections.

Unless otherwise specified, there will be no hypotheses testing for efficacy endpoints in the Post-Treatment Follow-up Period.

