11.3 Ranked Secondary and Other Efficacy Analyses

Ranked secondary efficacy endpoints during the Treatment Period include the following in the order specified below:

1. Change from Baseline in MBL volume to the Final Month;
2. Percentage of subjects with suppression of bleeding (no bleeding allowed, spotting allowed) at the Final Month;
3. Change from Baseline in MBL volume to Month 6;
4. Change from Baseline in MBL volume to Month 3;
5. Percentage of subjects with Baseline hemoglobin ≤ 10.5 g/dL who have an increase in hemoglobin > 2 g/dL at Month 6;
6. Change from Baseline in MBL volume to Month 1.

Other efficacy endpoints during the Treatment Period include the following:

- Change and percent change from baseline in MBL volume;
- Percentage of subjects with MBL volume < 80 mL and 50% or greater reduction in MBL volume from baseline during 28-day intervals throughout the Treatment Period;
- Percentage of subjects with amenorrhea;
- Percentage of subjects with control of bleeding;
- The number of bleeding days;
- Change and percent change from baseline in hemoglobin concentration;
- Patient Global Impression of Change (PGIC) questionnaire for Menstrual Bleeding and Non-Bleeding Uterine Fibroid Symptoms;
- Change and percent change from baseline in fibroid and uterine volume;
- Change from baseline for the UFS-QoL;
- Change from baseline for the EuroQoL-5D (EQ-5D-5L);
- The Health Care Resource Utilization (HCRU) questionnaire;
- Change from baseline for the WPAI.

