11.3.2.2 Suppression of Bleeding

Suppression of bleeding is defined similarly to amenorrhea as in Section 11.3.2 except that spotting is allowed. For each subject, achieving suppression of bleeding is defined as having 0 days of bleeding during the last 28 days prior to and including the Reference

Day with the interval starting from Study Day 11. The suppression of bleeding analysis will include subjects with at least 38 days prior to and including the Reference Day. If a subject did not have evaluable AH data during the last 28 days and no bleeding was indicated on UBQ ("Subject only has spotting that did not require the use of sanitary products" or "There was no visible blood on the sanitary products" was allowed), then the subject is considered having achieved suppression of bleeding.

The number and percentage of subjects achieving suppression of bleeding will be summarized by treatment group and will be compared between each of the elagolix dose groups and placebo using a Pearson's chi-square test or Fisher's exact test (if $\geq 20\%$ of the cells have expected counts less than 5).

Time to suppression of bleeding is defined as the number of days from the first study drug dose date to the day a subject achieving suppression of bleeding (i.e., the day a subject achieving suppression of bleeding – the first study drug dose date + 1). For a subject who achieved suppression of bleeding, the day she achieved suppression of bleeding is defined as the next day of the last bleeding day during the Treatment Period. The median, Q1, and Q3 of time to suppression of bleeding will be calculated using Kaplan-Meier method.

Monthly analysis of bleeding for suppression of bleeding, incidence and cumulative incidence of suppression of bleeding will be provided in the same way as was done for amenorrhea in [Table 9](#) and [Table 10](#). Plots will be provided by treatment group for percentage of subjects with incidence and cumulative incidence of suppression of bleeding during the Treatment Period, respectively.

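### Ranked secondary endpoint 5 (hemoglobin rise > 2 g/dL in anemic women) is tested without baseline adjustment, unlike comparable endpoints in the same SAP; the test is valid but may give up some power

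*SAP*

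**What the plan says.** SAP 11.3 lists as fifth of six ranked secondary endpoints: "Percentage of subjects with Baseline hemoglobin ≤ 10.5 g/dL who have an increase in hemoglobin > 2 g/dL at Month 6". SAP 11.3.4 gives its only analysis, a comparison of each elagolix group with placebo "using a Pearson's chi-square test or Fisher's exact test", with Fisher used when at least 20% of cells have an expected count below 5. Data are observed cases: "Hemoglobin (Hgb) concentration data will be summarized as observed; missing data will not be imputed". SAP 11.4 tests the ranked endpoints in a fixed sequence, so endpoint 5 gates only endpoint 6 (change in MBL volume to Month 1).

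Elsewhere the SAP adjusts for baseline:

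- The primary responder endpoint (11.2.2.1) uses logistic regression with baseline MBL volume.
- Continuous hemoglobin change, also in 11.3.4, uses ANCOVA with baseline.
- A reduction of at least 25% in fibroid or uterine volume (11.3.5.1) uses logistic regression with baseline volume.

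Protocol 8.1.7.2 allows CMH, chi-square, Fisher or logistic regression for categorical secondary endpoints. Neither document gives a subset size, response rate or power for endpoint 5.

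**The concern.** The endpoint is a threshold on change from baseline, so the Month 6 value a woman must exceed depends on where she starts. Exclusion criterion 8 (protocol 5.2.2) sets an entry floor near 8 g/dL, so the subset spans roughly 8 to 10.5 g/dL and the value to exceed runs from about 8 + 2 = 10 to 10.5 + 2 = 12.5 g/dL. Protocol 5.2.3.3 calls for iron in anemic women in every arm. That could plausibly pull Month 6 values toward a common level and make the gain depend on the start.

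Endpoint 5 is the only ranked endpoint limited by a baseline value, so it is very likely the smallest gated test. Randomization is unstratified (SAP 5.2), so nothing in the design balances baseline hemoglobin within this subset. An unranked volume endpoint gets a baseline-adjusted model while this ranked one does not. At stake are some power for endpoint 5 and, through the sequence, for endpoint 6.

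**Working it through.** **1. The plan's own figure.** SAP 4.3 says: "The sample size will provide at least 90% power to detect a difference", assuming "responder rates being 60% and 30% for elagolix 300 mg BID plus E2/NETA and placebo, respectively". This concerns the primary endpoint, with 100 placebo and 200 combination subjects and two-sided alpha 0.05. The pooled rate is (30 + 120)/300 = 0.50.

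- SE under the null = √[0.25 × (1/100 + 1/200)] = 0.0612
- SE under the alternative = √(0.21/100 + 0.24/200) = 0.0574
- z = (0.30 − 1.96 × 0.0612)/0.0574 = 3.13, so power is 99.9%

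The 90% floor is met. It says nothing about endpoint 5.

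**2. The SAP's test in the anemic subset.** All inputs here are assumptions. If 30% of women are anemic, the subset is 60 combination v 30 placebo; at 40% it is 80 v 40. If 30% are anemic and 80% of those have a Month 6 value, it is 48 v 24. With rates of 50% v 20% at 48 v 24, the pooled rate is (24 + 4.8)/72 = 0.40:

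- SEs are √[0.24 × (1/24 + 1/48)] = 0.1225 and √(0.16/24 + 0.25/48) = 0.1090
- z = (0.30 − 1.96 × 0.1225)/0.1090 = 0.55, so power is 70.9%

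From 24 v 12 to 64 v 32 women, with rates from 30% v 10% to 60% v 30%, chi-square power runs from about 23% to 84%. Subset size dominates.

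**3. When baseline matters.** Write Month 6 = arm mean + b × (baseline − 9.7) + error. Change then has slope b − 1 on baseline. With b = 0 (no tracking) the slope is −1 and baseline is strongly prognostic for change. With b = 1 (full tracking) it is 0 and baseline carries no information. The documents do not give b.

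**4. Simulation A.** Baseline N(10.3, 1.1) truncated to 8-10.5; arm means 11.9 v 11.1; residual SD 1.0; about 59% v 29-33% respond for b from 0 to 0.6; 1,500 to 2,000 trials per cell. The adjusted column is the likelihood-ratio (LR) test.

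| Combination v placebo | b | SAP test | Adjusted (LR) |
|---|---|---|---|
| 60 v 30 | 0 to 0.6 | 67-77% | 77-80% |
| 80 v 40 | 0 to 0.6 | 78-87% | 87-89% |
| 48 v 24 | 0 to 0.6 | 59-69% | 65-70% |
| 60 v 30 | 0.8 | 81.2% | 82.6% |
| 60 v 30 | 1.0 | 78.9% | 80.2% |
| 80 v 40 | 0.8 | 88.1% | 88.7% |
| 48 v 24 | 1.0 | 71.3% | 70.7% |

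The score test is close to LR (60 v 30, b from 0 to 0.6: 76-79%). Its gain over the SAP test is about 11 points at b = 0 and about 0 to 1 point at b = 0.8, slightly negative at 48 v 24. Null rejection was 4.5-7.1% for the score test and 4.0-6.5% for the SAP test. Monte Carlo error is about a point per cell: √(0.67 × 0.33/1500) = 0.012.

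**5. Simulation B: size, and which test.** Residual SD 1.3; baseline SD 0.64; change slope 0 to −1.0; 4,000 trials per cell. Power in %, SAP / LR / Wald:

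| Combination v placebo, rates | Slope 0 | Slope −0.5 | Slope −1.0 |
|---|---|---|---|
| 32 v 16, 40% v 15% | 42.1 / 45.7 / 28.2 | 41.6 / 46.6 / 29.3 | 42.8 / 52.4 / 33.2 |
| 48 v 24, 40% v 15% | 61.8 / 63.1 / 55.2 | 61.4 / 64.1 / 56.6 | 61.8 / 69.8 / 62.3 |
| 64 v 32, 50% v 20% | 84.0 / 84.7 / 83.2 | 84.9 / 87.1 / 85.1 | 84.6 / 89.6 / 87.9 |

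LR beats the SAP test even at slope 0, where the covariate is useless. LR is somewhat liberal here (null rejection 0.05-0.085) and the SAP test with its Fisher fallback is often conservative (0.026-0.052). Subtracting that excess at 48 v 24 gives (69.8 − 61.8) − (63.1 − 61.8) = 6.7 points at slope −1.0 and (64.1 − 61.4) − 1.3 = 1.4 points at slope −0.5. Across all cells the net gain is about 4-7 and 1.5-2 points respectively. Wald is up to 42.1 − 28.2 = 13.9 points worse than the SAP test at 32 v 16, and at best about 3 points better at 64 v 32.

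**The case against.** The SAP's choice is valid, is one of the methods the protocol lists, and has a small-cell safeguard in the Fisher rule. Endpoint 5 is fifth of six, so a failure blocks only endpoint 6, and 11.3.4 already gives a baseline-adjusted ANCOVA of hemoglobin change. The largest gain needs Month 6 hemoglobin to be unrelated to the woman's own baseline, which is the favourable extreme. With missing Month 6 values or stronger tracking the gain can vanish. All of this stands. It limits the size of the point but does not explain why a comparable dichotomised endpoint is adjusted and this one is not.

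Four stronger readings are tempting and not supported:

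- **That baseline decides who can respond.** Every woman in the subset can respond, since none needs to exceed 12.5 g/dL. The restriction to 10.5 g/dL and below has already narrowed the range to about 2.5 g/dL. Prognostic is as far as one can go.
- **That type I error is at risk.** It is not; randomization protects the unadjusted test.
- **That adjustment is free.** A Wald test can lose power in the smallest subsets, LR can be slightly liberal there, and dropping Fisher without a replacement removes a safeguard.
- **That ranked endpoint 2 needs the same change.** It too is compared with "placebo using a Pearson's chi-square test or Fisher's exact test" (SAP 11.3.2.2), but suppression of bleeding is not a threshold on change and is not confined to the anemic subset. No gain was shown for it.

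**Conclusion.** The point holds as one of efficiency and consistency. The gain from adjusting endpoint 5 for baseline hemoglobin is about 0 to 11 percentage points of power, assuming 30-40% of women are anemic and a residual SD of 1.0 g/dL. The upper end requires no tracking of Month 6 hemoglobin on baseline. At a tracking slope of 0.8 the gain is 0 to 1 point, and in small or noisy subsets it can be nil. The score-test results show that the larger gains are mainly real efficiency and not inflated size. Tracking, subset size, response rates and residual SD are all absent from the documents, so no single figure can be defended. Adjustment does not cure a small subset, which drives power far more.

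**What to change.** Amend SAP 11.3.4 before unblinding, for ranked endpoint 5 only:

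- Test by logistic regression with treatment and baseline hemoglobin (continuous).
- Name the score or likelihood-ratio test as the basis for the p-value, and rule out Wald.
- Specify a fallback for small cells or separation, such as Firth-penalised logistic regression or an exact method, with its trigger stated. The present expected-count rule could serve.
- Keep the chi-square/Fisher result as supportive.
- Report a standardized risk difference with its confidence interval, so that the effect stays on the scale of the endpoint.

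Leave ranked endpoint 2 as it is.

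The cost is SAP wording and slightly more programming. No new data are needed, and the covariate cannot be missing because it defines the subset. The protocol already allows logistic regression. The downsides are a conditional odds ratio as the model effect and, if LR is chosen, possibly slightly liberal size in very small subsets.

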11.3.5 Fibroid and Uterine Volume, FIGO Classification, Adenomyosis, and Post-Treatment Menses

11.3.5.1 Fibroid and Uterine Volume

Fibroid and uterine volume data will be summarized as observed; missing data will not be imputed. Analyses will be conducted separately for results obtained from TAU/TVU and MRI.

The change and percent change in the volume of the largest (primary) fibroid, the total fibroid volume (3 largest fibroids), and the uterine volume from Baseline to Month 3 (if applicable) and Month 6 during the Treatment Period will be summarized for each treatment group and compared between each elagolix dose group and placebo using an ANCOVA model with treatment as the main effect and Baseline as a covariate. The change and percent change at Post-Treatment Month 3 and Post-Treatment Month 6 (if applicable) during the Post-Treatment Follow-up Period will also be summarized for each treatment group.

The number and percentage of subjects with $\geq 25\%$ reduction from Baseline in total fibroid volume at Month 3 (if applicable) and Month 6 each during the Treatment Period will be summarized for each treatment group and analyzed using a logistic regression model, including treatment group as the main effect and Baseline volume as a covariate to compare each elagolix dose group to placebo. The same analysis will be performed for largest (primary) fibroid volume and uterine volume, respectively.

11.3.5.2 FIGO Classification

The number and percentage of subjects with fibroids at each location (e.g., intramural, subserosal, submucosal non-pedunculated, and subserosal pedunculated) according to the FIGO classification⁶ will be summarized for each treatment group at Baseline, Month 3 (if applicable) and Month 6 during the Treatment Period and Post-Treatment Month 3 and Post-Treatment Month 6 (if applicable) during the Post-Treatment Follow-up Period. No statistical test will be performed.

11.3.5.3 Adenomyosis

The number and percentage of subjects with presence of adenomyosis will be summarized for each treatment group at Baseline and each relevant post-baseline visit in the Treatment and Post-Treatment Follow-up Periods. Analyses above will be conducted separately for results obtained from TAU/TVU and MRI.

Baseline presence of adenomyosis is defined by considering available TAU/TVU or MRI results at Baseline (prior to or on Study Day 14). If a subject has adenomyosis results only from either TAU/TVU or an MRI at Baseline, then the Baseline adenomyosis is determined by that result; if a subject has adenomyosis results from both TAU/TVU and MRI at Baseline and they differ, then the MRI adenomyosis result is used. If a subject has multiple assessments of the same type (TAU/TVU, MRI), the results closest and prior to Study Day 1 will be used.

Additionally, the subset of subjects with adenomyosis identified at any point during the Baseline or Treatment Period will be defined as follows. If a subject has adenomyosis identified via TAU/TVU or MRI at any time during the Baseline or Treatment Period, the subject will be included in this set. This will include subjects who have differing results during the Treatment Period. Post-Treatment results will not be considered in the definition of this subset.

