11.2.4 Adenomyosis Subset

The proportion of responders and difference in proportions between each elagolix treatment group and placebo will be summarized as in the primary analysis for subjects with Baseline adenomyosis present, and repeated for the subjects with adenomyosis at any time during the Baseline or Treatment Period (see definition in Section 11.3.5.3). No statistical tests will be performed. This will be calculated using the same imputed datasets as in the primary analysis, subset for the subjects identified in the adenomyosis subset of interest.

For each of the adenomyosis subsets defined in Section 11.3.5.3, the statistical comparison between each elagolix dose group and placebo for subjects with Baseline adenomyosis present will be made using a logistic regression model including treatment as the main effect and Baseline MBL volume as a covariate in the integrated summary of efficacy (ISE) setting together data from Studies M12-815 and M12-817. The proportion of responders, difference in proportions between each elagolix treatment group and placebo and odds ratio with corresponding 95% CI, and p-values will be calculated. This will be calculated using the same imputed datasets as in the primary analysis for each respective study, subset for the subjects identified in the adenomyosis subset of interest.

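### Responder differences are planned in an adenomyosis subset defined partly by on-treatment scans, so randomization does not protect them, and the ISE sentence leaves unclear which subset is tested

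*SAP*

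**What the plan says.** SAP 11.3.5.3 defines two groups. The first is Baseline adenomyosis, from ultrasound or MRI up to and including Study Day 14. The second is an any-time group: "If a subject has adenomyosis identified via TAU/TVU or MRI at any time during the Baseline or Treatment Period", she belongs to it. The section adds: "This will include subjects who have differing results during the Treatment Period". One positive on-treatment scan is therefore enough, even after a negative baseline scan. Post-treatment scans do not count.

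For Study M12-815, SAP 11.2.4 summarizes responder proportions and elagolix-minus-placebo differences in the Baseline subset, and the summary is then "repeated for the subjects with adenomyosis at any time during the Baseline or Treatment Period". It states: "No statistical tests will be performed". SAP 11.3.1 extends the adenomyosis-subset analysis to each of the two response criteria, without saying which subset it means.

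SAP 11.2.4 then turns to inference "in the integrated summary of efficacy (ISE) setting together data from Studies M12-815 and M12-817". The sentence opens: "For each of the adenomyosis subsets defined in Section 11.3.5.3, the statistical comparison between each elagolix dose group and placebo". It goes on to restrict the comparison to women with adenomyosis present at Baseline. The planned output includes an "odds ratio with corresponding 95% CI, and p-values will be calculated".

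**The concern.** A subgroup comparison keeps the protection of randomization when membership is settled before treatment can influence it. The any-time set does not meet that condition for women whose first positive scan comes at Month 3, Month 6 or discontinuation. They enter on information gathered after randomization, and whether that information exists depends on how long they stayed.

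Staying is also tied to the outcome. Under SAP 11.2.1 and 11.2.2.1, stopping study drug for an adverse event, lack of efficacy, or surgery or invasive intervention makes a woman a non-responder whatever her blood loss. If she stops before Month 3 she also misses the later scans. If such stopping differs between arms, the any-time set removes non-responders unevenly.

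At stake is how a supplementary display is read: a difference in this set could be taken as the treatment effect in women with adenomyosis. I found no rationale for the set and no limit on its interpretation in either document.

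**Working it through.** The plan gives no figure for either adenomyosis subset, so there is none to reproduce. The sample-size statement concerns the whole trial.

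**Step 1: chances of detection.** Ultrasound is done at Screening (Protocol 5.3.1.1) and at Day 1, Month 3, and Month 6 or premature discontinuation (Protocol 1.2, Treatment Period Assessments).

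- A completer has four scheduled ultrasounds.
- A woman who stops between Month 3 and Month 6 has a discontinuation scan in place of Month 6, so also four.
- A woman who stops before Month 3 is not required to have the discontinuation ultrasound or MRI (Protocol Appendix C, footnote h), so she may have only two.

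MRI adds chances only for women who consent to the MRI subset.

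**Step 2: effect on detection.** Assume independent scans with per-scan sensitivity s. The chance of at least one positive in k scans is 1 − (1 − s)^k.

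| s (assumed) | 2 scans | 4 scans |
|---|---|---|
| 0.3 | 51% | 76% |
| 0.5 | 75% | 94% |
| 0.7 | 91% | 99% |

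For a woman without adenomyosis, at an assumed false-positive rate of 2%, 5% or 10% per scan, false inclusion rises from 4%, 10% or 19% with two scans to 8%, 19% or 34% with four.

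**Step 3: differential early stopping.** Assume 60% response in completers of both arms, no response in women who stop before Month 3, and early stopping of 20% on active and 5% on placebo. Among all women with adenomyosis the difference is 0.80 × 0.60 − 0.95 × 0.60 = 0.48 − 0.57 = −9.0 points. In the any-time set each group is weighted by its detection probability:

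response = (1 − d) × D4 × 0.60 / [(1 − d) × D4 + d × D2]

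Here d is the early-stopping rate, and D2 and D4 are the two-scan and four-scan detection probabilities.

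- s = 0.3: active 0.3648/0.7099 = 0.514; placebo 0.4331/0.7474 = 0.580; difference −6.6 points.
- s = 0.5: active 0.4500/0.9000 = 0.500; placebo 0.5344/0.9281 = 0.576; difference −7.6 points.

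The shift is 2.4 or 1.4 points. It is zero when early stopping is equal in both arms. If only pre-dose scans counted, every woman would have D2, the weights would cancel, and −9.0 would be recovered.

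**Step 4: treatment changing detection (hypothetical).** Assume no effect on response, equal numbers of severe and mild disease, and 40% detected before treatment. Of the rest, 50% are detected on treatment, except that mild disease on active falls to 25% or 0%. The weight of each type is 0.5 × (0.4 + 0.6 × on-treatment detection): 0.35 in general, and 0.275 or 0.20 for mild disease on active.

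- Response 20% severe, 40% mild: placebo 0.300; active 0.180/0.625 = 0.288 or 0.150/0.550 = 0.273. Spurious difference −1.2 or −2.7 points.
- Response 20% severe, 60% mild: placebo 0.400; active 0.235/0.625 = 0.376 or 0.190/0.550 = 0.345. Spurious difference −2.4 or −5.5 points.

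A subset fixed before treatment shows 0 in each case.

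**Step 5: the ISE sentence.** Its opening covers every subset in 11.3.5.3, which includes the any-time set. Its continuation names only women positive at Baseline. Both cannot hold, and nothing else in 11.2.4 settles it: the closing sentence refers only to the subset of interest.

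**The case against.** The plan is more careful than a quick reading suggests. The Baseline subset comes first and the any-time set is an addition. Within M12-815 the comparison is descriptive. Nothing here enters the primary endpoint, the six ranked secondary endpoints or the fixed-sequence procedure. The any-time set contains the baseline-positive women too, so only those added by later scans raise the issue. The loss of scans is confined mainly to stops before Month 3, and in the Step 3 illustration distorts the comparison only if early stopping differs by arm. All of this stands, and it keeps the point minor.

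A reader might infer three stronger things that the documents do not support.

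- **That p-values for the any-time set are definitely planned.** The opening words of the ISE sentence suggest it, but the continuation points to the Baseline subset. The ISE plan is not among the documents.
- **That treatment changes whether adenomyosis is seen.** No passage says so. SAP 11.3.5.3 only allows for results that differ on treatment. Step 4 is therefore a what-if; the follow-up route in Steps 1 to 3 needs no such assumption.
- **That the arms in this set are known to be non-comparable, in a known direction.** The documents show only that randomization no longer guarantees comparability.

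What the objection does not remove is that between-arm differences are still planned in a partly post-randomization set.

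**Conclusion.** The point holds as a minor one. Elagolix-minus-placebo responder differences in the any-time set are not protected by randomization, because membership depends partly on scans taken after treatment starts and on remaining long enough to have them, while several stopping reasons also determine the outcome. Separately, the ISE sentence in SAP 11.2.4 contradicts itself on which subset receives odds ratios and p-values.

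The documents give no prevalence, scan sensitivity or stopping rates by arm, so neither the direction nor the size of any bias can be determined. The shifts of 1.2 to 5.5 points above rest wholly on assumed inputs and show only that the mechanism can matter. No confirmatory conclusion or type I error depends on this analysis.

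**What to change.** 1. In SAP 11.2.4, in the component analyses of 11.3.1 and in the ISE, limit between-arm differences, odds ratios, confidence intervals and p-values to the Baseline subset.
2. Preferably define that subset from scans on or before Study Day 1, since the present window to Study Day 14 can admit scans taken after the first dose.
3. Report the any-time set only as counts by arm. SAP 11.3.5.3 already tabulates adenomyosis by arm and visit, so little is added.
4. Reword the ISE sentence to name the Baseline subset as the one tested, and say in 11.3.1 which subset is meant.

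The cost is one supplementary, possibly larger, subset display and its component analyses. Under item 2, a woman whose Day 1 MRI fell after Study Day 1 (Protocol Table 1 allows 7 days either side) would be classified on her earlier scans. The Baseline analysis is already planned, so no new data, visit or sample-size change is needed.
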